3.1.1 Overview of Study Design

This is a feasibility study which will evaluate the pre-operative treatment of DCIS of the breast with palbociclib. Patients with biopsy-proven DCIS are eligible for the study.

There will be 2 independent and unrelated study groups of 12 patients each, for a total of 24 patients:

- (a) Group A, of *male or female* patients treated with palbociclib single agent (n=12);
- (b) Group B, untreated, of *male or female* patients who consented translational studies in blood, as well as diagnostic and definitive surgical specimen, but not the pre-operative treatment with palbociclib (n=12).

Figure 3: Study schema

* Please refer to [Timing of Surgery](#) item below for details on scheduling for Group B.

Patients will be offered participation in the study at the diagnosis of DCIS (confirmed by pathology). Patients could consent biomarker and treatment (Group A) or biomarker-study only (Group B) activities. Once the patient is consented, archival tissue from the diagnostic biopsy will be obtained during screening and used for research in both Groups A and B. Positive Rb by immunohistochemistry in the DCIS component of the lesion will be required for participation on both Groups A and B. Patients consenting study participation will be referred to Medical Oncology clinic and undergo screening. After successful screening, patients enrolled on Group A will be treated preoperatively with palbociclib. **There will be no randomization.** The assignment to Group A or B is based on patient's choice. All patients consenting treatment on Group A will receive palbociclib alone. Since some patients may consent tissue collection, but not preoperative palbociclib treatment, Group B was created to acquire information about contemporary patients receiving biopsy followed by definitive surgery. This approach was first described by Stearns and Davidson⁵².

Choice of histology: a core biopsy showing DCIS-only will not rule out invasive disease. In some instances, invasive disease is found at definitive surgery. Since the proposed treatment will happen between diagnostic biopsy and definitive surgery, it is not practical to exclude from analysis patients

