4. MATERIALS AND METHODS

4.1 Patients

4.1.1 Inclusion Criteria

Inclusion criteria for all patients (Groups A and B):

Inclusion Criteria for all patients (Groups A and B)	
I.1	Signed informed consent obtained prior to any study specific assessments and procedures
I.2	Age ≥ 18 years
I.3	Premenopausal and postmenopausal women, or men
I.4	Current pathologic diagnosis of DCIS of the breast of any receptor status; History of previous DCIS allowed provided that the patient is currently off systemic risk-reduction endocrine therapy; History of previous invasive breast cancer adequately treated and that is currently in remission and unrelated to current DCIS (based on primary tumor location) is allowed as long as patient is currently off systemic therapy for that invasive cancer for at least 4 weeks prior to pre-treatment biopsy (diagnostic biopsy); Patients with multifocal or multicentric lesions are allowed, as long as at least one lesion

	is histologically confirmed DCIS and overall clinical AJCC Stage 0 or I.
I.5	A formalin-fixed paraffin-embedded (FFPE) tumor tissue block from diagnostic biopsy must be transmitted to MedStar Georgetown University Hospital Pathology Department repository and confirmation of receipt must be available prior to enrollment.
I.6	Positive Rb by immunohistochemistry in the DCIS component of the lesion Must be performed at CLIA-approved setting (for instance, MGUH) Rb staining will be considered positive when 1+ or above (in a scale of 0, 1+, 2+ or 3+)
I.7	In the absence of histologic diagnosis of DCIS, patient may undergo fresh biopsy for eligibility, provided: This invasive procedure is not a Fine Needle Aspiration (FNA); AND This procedure is a core biopsy, stereotactic biopsy or incisional biopsy of the suspicious breast lesion; AND The primary lesion is not completely resected during the procedure.
I.8	The patient is candidate for and is willing to receive definitive surgical therapy for DCIS
I.9	ECOG performance status 0-1 (Appendix G: ECOG PS scale).
I.10	Willingness to provide a sample of tissue collected at definitive surgery for research.

Inclusion criteria specific to treatment Group A:

Inclusion Criteria specific for patients enrolled on Group A	
I.11	Patients must be able and willing to swallow and retain oral medication
I.12	Absolute neutrophil count (ANC) $\geq 1,500/\text{mm}^3$
I.13	Platelets $\geq 120,000/\text{mm}^3$
I.14	Hemoglobin $\geq 10\text{g/dL}$

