6. STATISTICAL CONSIDERATIONS AND ANALYSIS PLAN

6.1 Determination of Sample Size

There will be two participating centers in this study: MGUH and MWHC. This is a prospective pilot study designed to assess the feasibility and potential translational changes of preoperative treatment with palbociclib of patients with Rb positive DCIS of the breast. The primary endpoints are feasibility and pathologic changes (histology, IHC and molecular analysis) comparing paired samples from before and after short course of systemic treatment (diagnostic core vs definitive surgery, in each patient). The secondary endpoint is descriptive toxicity.

The estimated sample size of 12 patients per study Group is decided based on typical sample size requirement for a pilot study⁵⁶ because parameters for expected pathologic changes caused by palbociclib in this disease are not available. *The total number of patients in this study will be 24.* The statistical analysis will be mostly descriptive due to the nature of the study and the small sample size. It will be performed after study completion. Baseline and follow-up data will be summarized using basic descriptive statistics such as means and standard deviations for the continuous variables and frequencies and percentages for categorical variables. For continuous outcome, the median and range will be reported. For binomial outcome, the proportion will be estimated along with its confidence interval estimated using exact method. Changes in the tumor histologic or molecular parameters from baseline to end of treatment will be tested using paired t-tests for continuous variables and McNemar's test for paired proportions. Repeated measures data will be analyzed using linear growth curve models that will allow us to identify and estimate individual-level growth tracks for the patients. Survival models (time to event) will be used as sample size permits to evaluate disease progression among all patients.

LCCC Biostat Unit will be responsible for designing the study and conducting data analysis which will be directed by [name].

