Appendix A: Study procedures

	Screening Phase		Treatment Phase		Pre-surgery	Surgery	Follow up Phase	
Procedure	Screening	Pre-treatment	Treatment start	Last day of treatment	Pre-surgery	Day of Surgery	End of Treatment visit	Long term follow up
Day	(-28 to -1)	(-28 to 0)	1	12	13 +/-1	15 +/-1	32 (+/- 8 days)	1yr and 5yr
Signed Informed Consent Form(s)	x							
Review of Eligibility Criteria	x	x						
Clinical Visit	x ⁹	x ⁷			x ⁷		x	
Review of breast US, Mammograms and breast MRI if available	x							
Disease status	x	x ⁴			x ⁴		x	x ⁶
CTCAE v. 4.03 review of baseline toxicities		x			x ⁴		x	
Archival tumor tissue specimen or 15 unstained slides	x							
Rb testing archival tissue	x ¹							
Tissue for research at definitive surgery						x ⁵		
CBC/diff/platelets	x ⁸	x ⁴			x ⁴		x	
CMP	x ⁸	x ⁴			x ⁴		x	
Coags (aPTT, INR)	x ⁸							
Serum or urine pregnancy test	x							
Blood sample for research - cells		x ²			x ^{2,4}		x ²	

	Screening Phase		Treatment Phase		Pre-surgery	Surgery	Follow up Phase	
Procedure	Screening	Pre-treatment	Treatment start	Last day of treatment	Pre-surgery	Day of Surgery	End of Treatment visit	Long term follow up
Day	(-28 to -1)	(-28 to 0)	1	12	13 +/-1	15 +/-1	32 (+/- 8 days)	1yr and 5yr
Schedule definitive surgery date		x						
Group A: Start palbociclib			x ³					
Group B: no treatment								
Lumpectomy or mastectomy						x		
Pathologic exam of specimen						x		
EMR review							x	1yr and 5yr
Telephone contact							x	1yr and 5yr

1 Rb testing for all participants at screening. Rb negative configures screen failure.

2 Research blood sample for liquid biopsy and tissue banking (serum/plasma and PBMCs). In Group B, pre-operative sample can be drawn any time after consenting and prior to surgery. For details on these samples please refer to item **4.5.2.7 Mandatory Blood Samples for Biomarker Analysis**

3 Palbociclib 100mg PO daily for 12 days; provided by Pfizer and to be dispensed by MGUH/WHC research pharmacy.

4 Group A only.

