5 Tissue sample #2: Under supervision of the certified pathologist, the sample required for pathologic diagnosis will be collected. Excess tissue will be used for research. Research tumor samples will be collected for H&E and IHC (formalin), CRC cultures (conditionally reprogrammed cell media), isolation of RNA and subsequent expression analysis, and for proteomic or metabolomic analysis (Snap Frozen). Non used tissue will be banked. Handling, processing, storage and testing DCIS sample at definitive surgery by pathologist and at Lombardi Research Lab ([name] LAB)

6 Evaluation of clinical characteristics including disease status by EMR review and telephone contact

[figure not shown]
7 Additional visits will be required for patients enrolled on Group A. These include a visit with Medical Oncology team prior to initiation of palbociclib (pre-Treatment) and another visit after end of palbociclib, prior to surgery (pre-Surgery). These visits are not required for patients enrolled in Group B.

8 Tests must be completed at least 5 days prior to definitive surgery in Group B (untreated)

9 Clinical visit -(28) to (-1) is the routine visit typically with the surgeon to discuss newly diagnosed DCIS and surgical plan, at which point the study may be offered to the patient (Group A and B).

[figure not shown]

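### Where a molecular assay uses FFPE tissue at baseline and frozen tissue at surgery, the planned within-group paired test cannot separate drug effect from preservation effect

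*Combined protocol and SAP*

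**What the plan says.** **Endpoint and test.** Section 6.1: "The primary endpoints are feasibility and pathologic changes (histology, IHC and molecular analysis) comparing paired samples from before and after" the short course of treatment. Molecular analysis is a separate item from IHC. The same section adds: "Changes in the tumor histologic or molecular parameters from baseline to end of treatment will be tested using paired t-tests for continuous variables", with McNemar's test for paired proportions.

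**Pairing rule.** Section 2.3 (Correlative science) compares Sample #1, the diagnostic core, with Sample #2, from definitive surgery, in the same patient and within each group. It states that Groups A and B will not be compared on translational changes.

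**Baseline tissue.** Criterion I.5 in section 4.1.1: "A formalin-fixed paraffin-embedded (FFPE) tumor tissue block from diagnostic biopsy must be transmitted to MedStar Georgetown University Hospital Pathology Department repository". Section 3.1.1: "archival tissue from the diagnostic biopsy will be obtained during screening and used for research in both Groups A and B". The Appendix A table lists "Archival tumor tissue specimen or 15 unstained slides". No section provides for a frozen or cultured baseline aliquot. Section 4.5.2.1 says the trial is typically offered after the diagnosis has been made, so the core has usually been processed by then.

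**Surgical tissue.** Appendix A footnote 5 uses tissue left over from diagnosis. It assigns formalin to H&E and IHC and a special medium to cell cultures, and then lists "isolation of RNA and subsequent expression analysis, and for proteomic or metabolomic analysis (Snap Frozen".

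**The concern.** A paired test attributes the mean within-patient difference to whatever changed between the two samples. In Group A, palbociclib is one change. For an assay run on frozen surgical tissue, preservation is another, because the only baseline is formalin-fixed. If the assay reads differently on the two kinds of tissue, the test can report a drug effect where there is none, or hide a real one.

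Section 1.3.2 says this study exists to generate human data for designing a larger efficacy study. A false or hidden molecular signal would carry into that decision.

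**Working it through.** **1. Tissue at each time point (4.1.1, 3.1.1, Appendix A)**

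| Work | Sample #1 | Sample #2 | Same preservation? |
|---|---|---|---|
| H&E, IHC markers | FFPE | formalin | yes |
| Proteomic or metabolomic | FFPE archive only | snap frozen | no |
| RNA expression | FFPE archive only | medium not clear | cannot tell |
| Cell cultures | FFPE archive only | culture medium | no |

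**2. What the paired mean estimates**

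Let θ be the drug effect and β the shift from FFPE to frozen.

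- Group A mean change = θ + β
- Group B mean change = β
- A minus B = θ, if β is the same in both groups

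The planned Group A test is a test of θ + β = 0. Only the A-minus-B contrast isolates θ, and section 2.3 excludes it.

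**3. Size of the effect on the test**

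Inputs from section 6.1: 12 patients per group, 2 × 12 = 24 in total. The 12 is a pilot rule of thumb with no alpha, power, effect or SD behind it, so there is no power figure to reproduce. Assumptions made here because the documents give neither: two-sided alpha 0.05, and effects expressed in SDs of the within-patient difference.

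- Paired t-test: reject when |T| exceeds the 0.975 quantile of t with 11 df, where T is noncentral t with noncentrality δ√12 = 3.464δ and δ = θ + β.
- A-minus-B contrast of changes: 22 df, noncentrality θ√(12/2) = 2.449θ.

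With no drug effect (θ = 0):

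| Preservation shift β (SD) | Noncentrality | Paired test significant |
|---|---|---|
| 0 | 0 | 5% |
| 0.25 | 0.866 | 12% |
| 0.5 | 1.732 | 35% |
| 0.75 | 2.598 | 66% |
| 1.0 | 3.464 | 88% |
| 1.5 | 5.196 | over 99% |

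In the other direction, a 1 SD drug effect met by a 1 SD shift of opposite sign gives δ = 0. Rejection is then 5%, against 88% without the shift.

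A simulation of 100,000 trials with no drug effect agrees. Untreated Group B gives 35% at β = 0.5 and 88% at β = 1.0, the same as Group A. The A-minus-B contrast stays at 4.9% to 5.1% throughout.

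**4. What each remedy leaves**

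| True drug effect (SD) | FFPE to FFPE, paired, n = 12 | A minus B, 12 vs 12 |
|---|---|---|
| 0.5 | 35% | 22% |
| 0.75 | 66% | 42% |
| 1.0 | 88% | 65% |
| Effect for 80% power | 0.89 SD | 1.20 SD |

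Like-for-like pairing removes the FFPE-to-frozen shift and has more power than the contrast between groups.

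**The case against.** *The documents never say that the primary molecular analysis means the RNA, proteomic or metabolomic work.* Section 2.3 (Pathology) mentions molecular changes and then says the biological markers are tested by IHC. Section 2.2.2 makes correlative science secondary, and footnote 5 ties no assay to an endpoint. This stands. A reader might infer that part of the primary endpoint cannot be answered, but the text supports only an undefined term. Calling the assays secondary does not remove the problem, because the Correlative science paragraph uses the same within-group pairing.

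*Preservation is tied to time point, not to treatment.* Also correct. Group B has the same archival-then-surgical handling, so a reader who infers that preservation is wholly confounded with treatment, or that no analysis could separate them, goes too far. The A-minus-B contrast would do so for a shared shift. The plan gives it up: section 2.3 excludes it for translational changes, although the feasibility criterion in that section mentions treated versus untreated specimens. It would also be imperfect, since patients choose their group (section 3.1.1) and selection bias would remain.

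*RNA may not be frozen.* The bracketed label in footnote 5 follows the proteomic and metabolomic item, and its reach back to RNA is unclear. The point is therefore not asserted for RNA.

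*The stakes are limited.* The analysis is mostly descriptive, with 12 per group. The frozen work uses excess tissue only, and the Appendix L form allows for no research sample at all. This limits the seriousness, but section 6.1 still plans formal tests.

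**Conclusion.** The point holds in conditional form. Section 6.1 names paired molecular change as primary and tests it, section 2.3 fixes the pairing within group, and the planned tissue is FFPE at baseline and snap frozen at surgery for proteomic or metabolomic work. Following those rules for such an assay gives a contrast that mixes drug and preservation.

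The bias cannot be sized from the documents. Under the stated assumptions, shifts of 0.25 to 1.0 SD raise the false-positive rate from 5% to between 12% and 88%. These figures illustrate how sensitive the test is; they do not predict the shift.

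Histology and the IHC markers are formalin-fixed at both time points and are not affected. The wording should be corrected before any molecular analysis, but the point does not undermine the study as a whole.

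**What to change.** - **Sections 6.1 and 2.3 (Pathology and Correlative science paragraphs):** name the primary molecular assays. Limit paired tests to assays run on formalin-fixed tissue at both time points, as far as the archival block or slides and the formalin surgical tissue allow. Both sections must change; amending 6.1 alone would leave the pairing rule of 2.3 in force.
- **Same sections:** label snap-frozen and cultured work as unpaired, single-time-point and exploratory.
- **Appendix A footnote 5:** state the preservation medium for RNA.

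**Cost.** No added patients or procedures. No before-after claim can be made from frozen assays. The FFPE molecular assays depend on the tissue left after Rb testing and IHC. The baseline may be only 15 slides, and footnote 5 currently earmarks the formalin surgical tissue for H&E and IHC. The documents do not show that enough remains, so the sponsor should confirm this before naming the assays.

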Appendix B: Study schema

Group A – Palbociclib treatment:

§ Please refer to item 4.5.2.7 Mandatory Blood Samples for Biomarker Analysis

Group B – tissue only:

[figure not shown]

* Please refer to item **3.1.1 Overview of Study Design, timing of surgery**, for additional details on definitive surgery timing after enrollment for patients on Group B (no palbociclib).

§ Please refer to item **4.5.2.7 Mandatory Blood Samples for Biomarker Analysis**

Appendix C: Calendar for treatment planning based on surgery date for Group A patients

Appendix D: Enrollment Process to Treatment Overview

Appendix E: Eligibility Checklist

Study Title: Palbociclib in patients with DCIS of the breast that are candidates for surgery

Patient Initials: _____

Study ID (IRB#): **2018-0075**

TO THE INVESTIGATOR, PLEASE CHECK BELOW IF YOU AGREE:

() Eligibility reviewed and confirmed by investigator, to be reviewed by LCCC PM

Enrolling MD (Print name): _____

Signature: _____ Date _____ / _____ / _____

Inclusion Criteria				
#	YES	NO	N/A	For all patients (both Groups A and B)
I.1				Signed informed consent obtained prior to any study specific assessments and procedures
I.2				Age \geq 18 years
I.3				Premenopausal and postmenopausal women or men
I.4				Current pathologic diagnosis of DCIS of the breast of any receptor status; a) History of previous DCIS allowed provided that the patient is currently off systemic risk-reduction endocrine therapy; b) History of previous invasive breast cancer adequately treated and that is currently in remission and unrelated to current DCIS (based on primary tumor location) is allowed as long as patient is currently off systemic therapy for that invasive cancer for at least 4 weeks prior to pre-treatment biopsy (diagnostic biopsy); c) Patients with multifocal or multicentric lesions are allowed, as long as one lesion is histologically confirmed DCIS and overall clinical AJCC Stage I.
I.5				A formalin-fixed paraffin-embedded (FFPE) tumor tissue block from diagnostic biopsy must be transmitted to MedStar Georgetown University Hospital Pathology Department repository and confirmation of receipt must be available prior to enrollment.

Inclusion Criteria (continuation)

#	YES	NO	N/A	For all patients (both Groups A and B)
I.6				
Positive Rb by immunohistochemistry in the DCIS component of the lesion
 
 a) Must be performed at CLIA-approved setting (for instance, MGUH) b) Rb staining will be considered positive when 1+ or above (in a scale of 0, 1+, 2+ or 3+)
I.7				
In the absence of histologic diagnosis of DCIS, patient may undergo fresh biopsy for eligibility, provided:
 
 a) This invasive procedure is not a Fine Needle Aspiration (FNA); AND b) This procedure is a core biopsy, stereotactic biopsy or incisional biopsy of the suspicious breast lesion; AND c) The primary lesion is not completely resected during the procedure.
I.8				The patient is candidate for and is willing to receive definitive surgical therapy for DCIS
I.9				ECOG performance status 0-1 (Appendix G: ECOG PS scale).
I.10				Willingness to provide a sample of tissue collected at definitive surgery for research.

Inclusion Criteria

#	YES	NO	N/A	Specific for patients enrolled on Group A
I.11				Patients must be able and willing to swallow and retain oral medication
I.12				Absolute neutrophil count (ANC) $\geq 1,500/\text{mm}^3$
I.13				Platelets $\geq 120,000/\text{mm}^3$
I.14				Hemoglobin $\geq 10\text{g/dL}$
I.15				Total serum bilirubin $\leq \text{ULN}$; or total bilirubin $\leq 3.0 \times \text{ULN}$ with direct bilirubin within normal range in patients with documented Gilbert's Syndrome.

I.16				Aspartate amino transferase (AST or SGOT) and alanine amino transferase (ALT or SGPT) $\leq 1.5 \times$ institutional ULN
------	--	--	--	---

Inclusion Criteria (continuation)

#	YES	NO	N/A	Specific for patients enrolled on Group A
I.17				Serum creatinine within normal institutional limits or creatinine clearance $\geq 50 \text{ mL/min}/1.73 \text{ m}^2$ for patients with serum creatinine levels above institutional ULN.
I.18				
Pregnancy must be ruled out:
 
 a) Serum or urine pregnancy test must be negative within 14 days of treatment start in women of childbearing potential. b) Pregnancy testing does not need to be pursued in patients who are judged as postmenopausal before enrollment, or who have undergone tubal ligation, bilateral oophorectomy, total hysterectomy
I.19				
Willingness to undergo adequate contraception if childbearing potential
 
 a) Women of childbearing potential and male patients randomized into treatment Group A must use adequate contraception for the duration of protocol treatment and for 3 months after the last treatment with palbociclib if they are in Group A. b) Adequate contraception is defined as one highly effective form (i.e. abstinence, (fe)male sterilization) OR two effective forms (e.g. non-hormonal IUD and condom / occlusive cap with spermicidal foam / gel / film / cream / suppository).

Exclusion Criteria

#	YES	NO	N/A	For all patients (both Groups A and B)
E.1				Concurrent therapy with other Investigational Products.
E.2				
Invasive carcinoma present in the diagnostic biopsy
 
 • Microinvasion is allowed
E.3				Uncontrolled intercurrent illness including (active infection, symptomatic congestive heart failure, unstable angina pectoris, cardiac arrhythmia, diabetes, pulmonary embolism in the past 6 months, or psychiatric illness/social situations that would limit compliance with study requirements).

E.4				Unable to comply with study requirements
E.5				Hormone therapies containing estrogen, progesterone, GnRH agonists and antagonists within 4 weeks from diagnostic biopsy.
E.6				Therapy with any CDK inhibitor in the past 3 months

Exclusion Criteria

#	YES	NO	N/A	Specific for patients enrolled on Group A
E.7				History of allergic reactions attributed to compounds of chemical or biologic composition similar to palbociclib
E.8				Presence of a condition that would interfere with enteric absorption of palbociclib
E.9				Pregnant women, or women of childbearing potential without a negative pregnancy test (serum or urine) within 7 days prior to enrollment 
 . Breastfeeding must be discontinued prior to study entry (Group A only).
E.10				Patients on combination antiretroviral therapy, i.e. those who are HIV+ (potential for pharmacokinetic interactions or increased immunosuppression with palbociclib).
E.11				Patients receiving any medications or substances that are potent inhibitors or inducers of CYP3A isoenzymes within 7 days of enrollment or during participation on study (see Section 4.4.5 Prohibited Therapy for list of CYP3A inhibitors and inducers).
E.12				Patients with clinically significant history of liver disease, including viral or other known hepatitis, current alcohol abuse, or cirrhosis, etc.

PLEASE SCAN THIS COMPLETED FORM TO THE PATIENT'S ELECTRONIC MEDICAL RECORD

